9.3.2 Safety Analyses

All safety analyses will be performed on the safety analysis set separately for each cohort. In Cohort A, subjects who are dMMR will be evaluated together with pMMR subjects.

Treatment-emergent adverse events are defined as AEs that first occurred or worsened in severity after the first administration of study treatment and prior to 30 days after the last administration of study treatment.

Adverse events will be coded using the Medical Dictionary for Regulatory Activities (MedDRA). Numbers of TEAEs and incidence rates will be tabulated by preferred term and system organ class.

Treatment-emergent AEs of any grade, TEAEs with severity \geq Grade 3 (NCI-CTCAE v 5.0), TEAEs (any grade) by relationship to study treatment, TEAEs related (probable, possible or unknown causality) to study treatment with severity \geq Grade 3 (NCI-CTCAE v 5.0) SAEs, TEAEs leading to death, and TEAEs leading to discontinuation of study treatment will be tabulated for the number and proportion of subjects. Additionally, treatment tolerability will be determined by the number of study discontinuations due to treatment-related TEAEs. Commonly occurring TEAEs,

ie, those that occur in 5% or more of the subjects in either treatment group, will be summarised using descriptive statistics.

All laboratory test results, vital signs measurements, ECG results, weight, and body mass index will be summarised using descriptive statistics at each visit for raw numbers and change from baseline. The incidence of treatment-emergent abnormal laboratory, vital sign, and ECG values will also be summarised using descriptive statistics.

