1.0 PROTOCOL SUMMARY

1.1 Synopsis

Protocol Title: Phase IIa open-label clinical study of intratumoural administration of BO-112 in combination with pembrolizumab in subjects with liver metastasis from colorectal cancer or gastric/gastro-oesophageal junction cancer.

Short Title: Study of BO-112 with pembrolizumab for colorectal or gastric/GEJ cancer with liver metastasis.

Rationale:

Checkpoint inhibition provides significant clinical benefit in various types of cancer, with blockade of the programmed cell death protein 1(PD1) receptor and its ligands being the most widely used approach. Some tumours, however, evade the immune system and are not, or only poorly, responsive to checkpoint inhibition. The innate immune system interacts with the adaptive immune system and responds to different triggers. The purpose of this study is to evaluate if the combination of activation of the innate immune system and blockade of the PD1 immune checkpoint can provide clinical benefit in patients with tumours that are poorly, or only moderately responsive to monotherapy with an anti-PD1 agent. Activation of the innate immune system will be via direct intratumoural (IT) administration of BO-112. Checkpoint inhibition will be via intravenous infusion of pembrolizumab. Metastatic liver lesions have been selected as the site for intratumoural injection for 2 reasons: to reduce the variability of the microenvironment of the injection site, and to evaluate if the TLR3 agonist activity of BO-112 potentially breaks through the generally immune-tolerant hepatic microenvironment.

Study Objectives and Endpoints

Objectives	Endpoints
Primary	
 Investigation of the anti-tumour efficacy and safety of repeated IT administrations of BO-112 in metastatic liver lesions in combination with IV pembrolizumab

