Secondary	
 Efficacy: ORR based on the BOR using RECIST 1.1 Safety: number and proportion of subjects with study treatment-related TEAEs with severity \geq Grade 3 (NCI-CTCAE v 5.0) Further characterisation of safety and of clinical activity of the combination as well as determination of systemic exposure of BO-112 Safety: number and proportion of subjects with TEAEs (any grade) Safety: number and proportion of subjects with related TEAEs (any grade) Tolerability: number of study discontinuations due to related TEAE Efficacy: disease control rate (DCR = CR, PR and SD of at least 12 weeks duration) using RECIST 1.1 Efficacy: ORR based on best overall response using RECIST modified for immune-based therapies (iRECIST) Efficacy: DCR = iCR, iPR + iSD of at least 12 weeks duration) using iRECIST Efficacy: duration of response Efficacy: progression-free survival Efficacy: overall survival rate at 6 months Pharmacokinetics: systemic exposure after first BO-112 administration
Exploratory	
 Evaluation of antitumoural and immunological effects in the TME of the injected lesion. Immune cell profile of TME in injected and noninjected lesions Genetic analysis of the TME

Abbreviations: BOR=best overall response; CR= complete response; DCR=disease control rate; iRECIST= RECIST modified for immune-based therapies; IT=intratumoural; NCI-CTCAE=National Cancer Institute-Common terminology criteria for adverse events; ORR=objective response rate; PR= partial response; RECIST= Response evaluation criteria in solid tumours; SD=stable disease; TEAE=treatment-emergent adverse event; TME=tumour microenvironment.

Note: the prefix “i” denotes immune-related or immune-based.

Overall Design:

[figure not shown]
This is an open-label, Phase II, non-comparative, 2-cohort study with a Simon's 2-stage design.

Cohort A: colorectal cancer (CRC)

Cohort B: gastric or gastro-oesophageal junction cancer (GC/GEJ)

Subjects will be enroled in each cohort for Stage 1 of the study up to the predefined sample size and treated according to the treatment schedule. Enrolment will be suspended per cohort and a Data Monitoring Committee (DMC) will review the safety and efficacy data available at the time that the last subject enroled has reached the first on-study response assessment at Week 7 (= Cycle 3). The DMC will make a recommendation to the Sponsor for each cohort regarding expanding to the total foreseen sample size.

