The safety profile of pembrolizumab as a single agent is characterised by: fatigue, musculoskeletal pain, decreased appetite, pruritus, diarrhoea, nausea, rash, pyrexia, cough, dyspnoea, constipation, pain and abdominal pain (ie, reported in $\geq 20\%$ of patients). In addition, immune-related AEs (irAEs) may occur shortly after the first dose or several months after the last dose of pembrolizumab treatment and may affect more than 1 body system simultaneously. Therefore, early recognition and initiation of treatment is critical to reduce complications. Based on existing clinical study data, most irAEs were reversible and could be managed with interruptions of pembrolizumab, administration of corticosteroids and/or other supportive care (for more details see Section 1.1 and Table 5).

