8.3.1 Time Period and Frequency for Collecting AE and SAE Information

- All AEs or ECIs (Events of Clinical Interest) from the time of treatment start through 30 days following cessation of study treatment must be reported by the investigator. All AEs will be collected at the time points specified in the SoA (Section 1.3).
- All AEs meeting serious criteria, from the time of treatment start through 90 days following cessation of study treatment, or 30 days following cessation of study treatment if the participant initiates new anticancer therapy, whichever is earlier must be reported by the investigator. All SAEs will be collected at the time points specified in the SoA (Section 1.3).
- All pregnancies and exposure during breastfeeding, from the time of treatment/ allocation through 120 days following cessation of study treatment, or 30 days following cessation of study treatment if the participant initiates new anticancer therapy must be reported by the investigator.

Medical occurrences that begin before the start of study treatment but after obtaining informed consent will be recorded on the medical history/Current Medical Conditions section of the ECRF, not the AE section.

All SAEs will be recorded and reported to the Sponsor or designee within 24 hours, as indicated in [Appendix 4](#). The investigator will submit any updated SAE data to the Sponsor within 24 hours of it being available.

Investigators are not obligated to actively seek AE or SAE after conclusion of the study participation. However, if the investigator learns of any SAE, including a death, at any time after a subject has been discharged from the study, and he/she considers the event to be reasonably related to the study treatment or study participation, the investigator must promptly notify the Sponsor.

The method of recording, evaluating, and assessing causality of AE and SAE and the procedures for completing and transmitting SAE reports are provided in [Appendix 4](#).

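### The primary safety rate stops counting 30 days after last dose although SAEs must be reported to day 90, so it can understate related Grade ≥3 toxicity; a second rate over the SAE window should be prespecified

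*Combined protocol and SAP*

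**What the plan says.** The primary objective in the Synopsis (section 1.1) covers safety as well as efficacy: "Investigation of the anti-tumour efficacy and safety of repeated IT administrations of BO-112 in metastatic liver lesions", given with IV pembrolizumab. The safety endpoint listed next to ORR by RECIST 1.1 is the "number and proportion of subjects with study treatment-related TEAEs with severity" of Grade 3 or higher. The layout of that table is broken in the text available; I read this line as the primary safety endpoint because it stands with the primary ORR line.

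Section 9.3.2 limits TEAEs to events that first occur or worsen after the first administration and "prior to 30 days after the last administration of study treatment". The tabulations it lists include related Grade ≥3 TEAEs, fatal TEAEs and, without the TEAE label or any stated window, SAEs.

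Section 8.3.1 sets two collection periods. All AEs "from the time of treatment start through 30 days following cessation of study treatment must be reported by the investigator". For serious events the period is longer: "All AEs meeting serious criteria, from the time of treatment start through 90 days following cessation of study treatment". That longer period is cut short for a subject who moves on to another cancer treatment: "or 30 days following cessation of study treatment if the participant initiates new anticancer therapy, whichever is earlier".

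Section 2.2.2 says that immune-related events "may occur shortly after the first dose or several months after the last dose of pembrolizumab treatment", and section 6.3.1 repeats this.

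**The concern.** For serious events the analysis window is shorter than the collection window. Safety is part of the primary objective, late immune toxicity is a risk the protocol itself describes, and section 6.3.1 says it is not known whether BO-112 induces or potentiates immune-related events. Yet a serious, related, high-grade event in the second or third month after treatment has no place in the main safety rate. A related fatal event with onset in that period is likewise absent from the table of fatal TEAEs. With small cohorts, one or two such subjects would visibly change the reported proportion.

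**Working it through.** The plan states no rate, threshold or power for the safety endpoint, so there is no figure to reproduce. The check compares the windows and then works out what one omitted subject is worth.

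**Inputs**
- Endpoint window: onset or worsening before day 30 after last dose (9.3.2).
- Collection of all AEs: to day 30 (8.3.1).
- Collection of SAEs: to day 90, or day 30 on new anticancer therapy (8.3.1).
- Last scheduled visit: EOS, 28 days after last treatment (Table 1).
- Cohort sizes: 26 and 43 pMMR subjects, plus about 1 to 2 replaced dMMR subjects per cohort who stay in the safety set (9.1, Table 7).

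**Step 1: which related Grade ≥3 events count**

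| Onset after last dose | Collected? | In primary safety endpoint? |
|---|---|---|
| Day 20, serious or non-serious | Yes | Yes |
| Day 45, serious, no new anticancer therapy | Yes | No |
| Day 45, serious, new anticancer therapy started by then | No, window ends at day 30 | No |
| Day 45, non-serious | No | No |

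The second row is the gap. It runs from day 30 to day 90, so 90 − 30 = 60 days at most per subject.

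**Step 2: direction**

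Let A be the subjects with a related Grade ≥3 TEAE, and B those with a related Grade ≥3 SAE in the gap. The rate over the full window is |A ∪ B| / n and the planned rate is |A| / n. Since |A ∪ B| ≥ |A|, the planned rate equals or falls below the fuller one. They differ only through subjects in B who are not in A, that is, with no earlier qualifying event.

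**Step 3: size per subject (1/n)**
- Cohort A: 1/26 = 3.8%; with two added dMMR subjects, 1/28 = 3.6%.
- Cohort B: 1/43 = 2.3%; with two added dMMR subjects, 1/45 = 2.2%.
- If a cohort stops after Stage 1 (11 or 18 pMMR subjects): 1/11 = 9.1% and 1/18 = 5.6%.

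**Step 4: illustration under an assumed frequency**

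The documents give no value for q, the share of subjects whose only qualifying event falls in the gap. For q of 1%, 3% and 5%, the expected number omitted is nq and the chance of omitting at least one is 1 − (1 − q)^n.

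| Assumed q | Cohort A (n = 26): expected; chance of ≥1 | Cohort B (n = 43): expected; chance of ≥1 |
|---|---|---|
| 1% | 0.26; 23% | 0.43; 35% |
| 3% | 0.78; 55% | 1.29; 73% |
| 5% | 1.30; 74% | 2.15; 89% |

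These rows show sensitivity to an unknown input and are not predictions.

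**The case against.** The best defence is that the 30-day limit matches the period in which all AEs are collected. Within it, serious and non-serious Grade ≥3 events are ascertained alike. Moving the primary endpoint to day 90 would mix windows: 90 days for serious events, 30 for non-serious events, and 30 for anyone starting new therapy. Capture beyond day 30 is also weaker. No visit is scheduled after EOS, and section 8.3.1 does not oblige investigators to seek events actively once participation ends. This stands as a reason not to redefine the primary endpoint. It does not argue against a second rate shown beside it.

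Two stronger readings are tempting. A reader might infer that late serious events vanish from the report. The documents do not support this: section 9.3.2 tabulates SAEs without a TEAE restriction and section 9.3 puts individual data in listings. What is missing is a rate that combines relatedness and grade over the longer window, and a stated window for the SAE table. A reader might also infer that the omission biases a test of whether BO-112 adds to pembrolizumab toxicity. There is no such test: the study is non-comparative and has no safety hypothesis.

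Finally, section 9.3 calls itself a summary and leaves detail to an SAP whose text is not in the document. That SAP could contain the extra table, but nothing in section 9.3.2 commits to it.

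**Conclusion.** The point holds in a limited form. As defined, the primary safety endpoint and the fatal-TEAE table cannot count a related SAE with onset from day 30 to day 90, although section 8.3.1 requires it to be reported unless new anticancer therapy has shortened the window. The direction is certain: the headline rate equals or understates the rate over the SAE window. The amount is unknown. It is 3.6 to 3.8 points in Cohort A and 2.2 to 2.3 points in Cohort B for each subject with no earlier qualifying event, assuming full enrolment and up to two dMMR subjects added per cohort. It would be wrong to say that every late event moves the rate, or that immune-related events generally arise late; the protocol says only that they may. The Simon design and the ORR analysis are unaffected. This is an inexpensive improvement to safety reporting and does not make the primary endpoint invalid.

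**What to change.** Keep the 30-day TEAE endpoint as it is. In section 9.3.2, and in the SAP:

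1. Prespecify beside it, for each cohort, the number and proportion of subjects with either a related Grade ≥3 TEAE or a related Grade ≥3 SAE with onset within the section 8.3.1 SAE window (day 90, or day 30 if new anticancer therapy starts).
2. State that same window explicitly for the SAE table and the death table.
3. Note under the tables that non-serious events after day 30 are not collected, and that capture after the 28-day EOS visit relies on investigator reporting without a scheduled visit.

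The cost is one extra table and two window definitions, using data the protocol already requires. The companion rate may be slightly higher than the 30-day rate, and because it mixes windows it should be labelled as supplementary.

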9.3.3 Other Analyses

Biomarker exploratory analyses will be described in the SAP. Pharmacokinetic analyses are expected to be limited since no systemic exposure is expected from IT injection of BO-112. There will be no PK analysis of pembrolizumab. Therefore, the PK analysis will be described in the SAP.

9.3.4 Missing, Unused and Spurious Data

Statistical analysis will be performed using available data only; missing values will not be imputed. Data from subjects who withdraw from the study, including AEs and any follow-up, will be included in the analyses of primary and secondary outcomes.

9.4 Interim Analyses

An interim analysis for futility will be carried out in each cohort separately when the prespecified number of subjects for Stage 1 have been enroled and have reached at least the first on-study response assessment. Enrolment will be suspended per cohort at the Stage 1 sample size pending the outcome of the DMC review. The DMC will review the safety and efficacy data per cohort. The number of responses together with the ORR, DCR, number of subjects with Grade 3 to 5 AEs, SAEs and individual subject tumour burden profiles will be taken into account to make a reasoned recommendation to the Sponsor regarding extension of each cohort to the foreseen total number of subjects. The stopping rules for futility based on the observed number of responses are defined in Section 9.2 and considered non-binding, leaving the final recommendation for stopping the study after Stage 1 at the discretion of the DMC members

The SAP will describe the planned interim analyses in greater detail.

9.5 Data Monitoring Committee

A DMC consisting of members who are independent from the Sponsor will be established. The DMC membership will have 3 members, including specialists with expertise in CRC, gastric/GEJ cancer and immuno-oncology. The study statistician will provide statistical support.

When the prespecified number of subjects for Stage 1 have been enroled and have reached at least the first on-study response assessment, the DMC will review the safety and efficacy data per cohort. Enrolment will be suspended per cohort and the DMC will review the safety and efficacy data available at the time that the last subject enrolled has reached the first on-study response

assessment at Week 7 (= Cycle 3). The DMC will make a recommendation to the Sponsor separately for each cohort regarding expanding to the total foreseen sample size.

The DMC will be responsible for making recommendations as to whether it is scientifically and ethically appropriate to continue enrolment, discontinue treatment groups, or stop the study.

11.0 APPENDICES

Appendix 1**Abbreviations**

Abbreviation	Definition
AE	Adverse event
ALT	Alanine aminotransferase
AST	Aspartate aminotransferase
BOR	Best overall response
CI	Confidence interval
CR	Complete response
CRC	Colorectal cancer
CRO	Contract research organisation
CRP	C-reactive protein
CT	Computed tomography
CTCAE	Common Terminology Criteria for Adverse Events
DCR	Disease control rate
DMC	Data monitoring committee
dMMR	Deficient mismatch repair
DRE	Disease-related event
ECG	Electrocardiogram
ECOG PS	Eastern Cooperative Oncology Group Performance Status
eCRF	Electronic case report form
EGFR	Epidermal growth factor receptor
EOS	End of Study
GC/GEJ	Gastric or gastro-oesophageal junction cancer
GCP	Good Clinical Practice
ICF	Informed consent form
ICH	International Council for Harmonisation
iCPD	Confirmed progressive disease
IEC	Independent Ethics Committee
IFN	Interferon
Ig	Immunoglobulin
irAE	Immune-related adverse event
iRECIST	RECIST modified for immune-based therapies
IT	Intratumoural

Abbreviation	Definition
DNA	Deoxyribonucleic acid
iUPD	Immune unconfirmed progressive disease
IV	Intravenous (ly)
mAb	Monoclonal antibody
mPFS	Median progression-free survival
MSI	Microsatellite instability
MSI-H	Microsatellite instability-high
MSS	Microsatellite stability
NCI	National Cancer Institute
NSCLC	Non-small cell lung cancer
ORR	Objective response rate
PD1	Programmed cell death Protein 1
PDL	Programmed cell death ligand
PEI	Polyethyleneimine
PFS	Progression-free survival
PK	Pharmacokinetics
pMMR	Proficient mismatch repair
Poly I:C	polyinosinic-polycytidylic acid
PR	Partial response
Q2W	Once every 2 weeks
Q3W	Once every 3 weeks
RBC	Red blood cell
RECIST	Response evaluation criteria in solid tumours
SAE	Serious adverse event
SAP	Statistical Analysis Plan
SCCHN	Squamous cell carcinoma of the head and neck
SD	Stable disease
SoA	Schedule of Assessments
TEAE	Treatment-emergent adverse event
TME	Tumour microenvironment
ULN	Upper limit of normal
V	Visit

Abbreviation	Definition
W	Week
WOCBP	Woman of childbearing potential

Appendix 2 Regulatory, Ethical, and Study Oversight Considerations

Regulatory and Ethical Considerations

- This study will be conducted in accordance with the protocol and with the following:
 - Consensus ethical principles derived from international guidelines including the Declaration of Helsinki and Council for International Organisations of Medical Sciences (CIOMS) International Ethical Guidelines.
 - Applicable International Council for Harmonisation (ICH) Good Clinical Practice Guidelines.
 - Applicable laws and regulations.
- The protocol, protocol amendments, ICF, Investigator's Brochure, and other relevant documents (eg, advertisements) must be submitted to an IEC by the investigator and reviewed and approved by the IEC before the study is initiated.
- Any amendments to the protocol will require IEC and regulatory authority approval, when applicable, before implementation of changes made to the study design, except for changes necessary to eliminate an immediate hazard to subjects.
- The investigator will be responsible for the following:
 - Providing written summaries of the status of the study to the IEC annually or more frequently in accordance with the requirements, policies, and procedures established by the IEC.
 - Notifying the IEC of SAEs or other significant safety findings as required by IEC procedures.
 - Providing oversight of the conduct of the study at the study center and adherence to requirements of 21 Code of Federal Regulations (CFR), ICH guidelines, the IEC, European regulation 536/2014 for clinical studies (if applicable), and all other applicable local regulations.
- After reading the protocol, each investigator will sign the protocol signature page and send a copy of the signed page to the Sponsor or representative ([Appendix 10](#)). The study will not start at any study center at which the investigator has not signed the protocol.

Financial Disclosure

Investigators and sub-investigators will provide the Sponsor with sufficient, accurate financial information as requested to allow the Sponsor to submit complete and accurate financial certification or disclosure statements to the appropriate regulatory authorities. Investigators are responsible for providing information on financial interests during the course of the study and for 1 year after completion of the study.

Insurance

Sponsor will provide insurance in accordance with local guidelines and requirements as a minimum for the subjects in this study. The terms of the insurance will be kept in the study files.

Informed Consent Process

- The investigator or his/her representative will explain the nature of the study to the subject or his/her legally authorised representative and answer all questions regarding the study.
- Subjects must be informed that their participation is voluntary. Subjects will be required to sign a statement of informed consent that meets the requirements of local regulations, ICH guidelines, and the IEC or study center.
- The medical record must include a statement that written informed consent was obtained before the subject was entered in the study and the date the written consent was obtained. The authorised person obtaining the informed consent must also sign the ICF.
- Subjects must be re-consented to the most current version of the ICF(s) during their participation in the study.
- A copy of the ICF(s) must be provided to the subject or the subject's legally authorised representative.

A subject who is rescreened is not required to sign another ICF if the rescreening occurs within 28 days from the previous ICF signature date.

The ICF will contain a separate section that addresses the use of remaining mandatory samples for optional exploratory research. The investigator or authorised designee will explain to each subject the objectives of the exploratory research. Subjects will be told that they are free to refuse to participate and may withdraw their consent at any time and for any reason during the storage period. A separate signature will be required to document a subject's agreement to allow any remaining specimens to be used for exploratory research. Subjects who decline to participate in this optional research will not provide this separate signature.

Data Protection

- Subjects will be assigned a unique identifier by the Sponsor. Any subject records or datasets that are transferred to the Sponsor will contain the identifier only; subject names or any information which would make the subject identifiable will not be transferred.
- The subject must be informed that his/her personal study-related data will be used by the Sponsor in accordance with local data protection law. The level of disclosure must also be explained to the subject.
- The subject must be informed that his/her medical records may be examined by Clinical Quality Assurance auditors or other authorised personnel appointed by the Sponsor, by appropriate IEC members, and by inspectors from regulatory authorities.

- The ICF will incorporate (or, in some cases, be accompanied by a separate document incorporating) wording that complies with relevant data protection and privacy legislation.
- The Sponsor or its representative will not provide individual genotype results to subjects, any insurance company, any employer, their family members, general physician, or any other third party, unless required to do so by law.
- Extra precautions are taken to preserve confidentiality and prevent genetic data being linked to the identity of the subject. In exceptional circumstances, however, certain individuals might see both the genetic data and the personal identifiers of a subject. For example, in the case of a medical emergency, the Sponsor or representative physician or an investigator might know a subject's identity and also have access to his or her genetic data. Also regulatory authorities may require access to the relevant files.

Administrative Structure

Table 9 Study Administrative Structure – 3rd parties external to Sponsor

Activities	External Service Provider
Study Operations Management	Pivotal
Medical Monitoring	Pivotal
Study Master File	Pivotal
Data Management	IDDI
Clinical Supply Management	IDDI/Alcura
Biostatistics	IDDI
Medical Writing	IDDI
Laboratory Assessments	Local labs for safety parameters Covance and Pangaea labs for tumour biopsy samples
Pharmacokinetic Sample Testing	Accelero

Dissemination of Clinical Study Data

The results of the study should be reported within 1 year from the end of the clinical study. Irrespective of the outcome, the Sponsor will submit to the EU database a summary of the results of the clinical study within 1 year from the end of the clinical study. It shall be accompanied by a summary written in a manner that is understandable to laypersons.

Data Quality Assurance

- All subject data relating to the study will be recorded on printed or eCRFs unless transmitted to the Sponsor or designee electronically (eg, laboratory data). The investigator is responsible for verifying that data entries are accurate and correct by physically or electronically signing the eCRF.

- The investigator must maintain accurate documentation (source data) that supports the information entered in the eCRF.
- The investigator must permit study-related monitoring, audits, IEC review, and regulatory agency inspections and provide direct access to source data documents.
- The Sponsor or designee is responsible for the data management of this study including quality checking of the data.
- Study monitors will perform ongoing source data verification to confirm that data entered into the eCRF by authorised study center personnel are accurate, complete, and verifiable from source documents; that the safety and rights of subjects are being protected; and that the study is being conducted in accordance with the currently approved protocol and any other study agreements, ICH GCP, and all applicable regulatory requirements.
- Records and documents, including signed ICFs, pertaining to the conduct of this study must be retained by the investigator for 15 years after study completion unless local regulations or institutional policies require a longer retention period. No records may be destroyed during the retention period without the written approval of the Sponsor. No records may be transferred to another location or party without written notification to the Sponsor.

Source Documents

The investigator/institution should maintain adequate and accurate source documents and study records that include all pertinent observations on each of the study center's subjects. Source data should be attributable, legible, contemporaneous, original, accurate, and complete. Changes to source data should be traceable, should not obscure the original entry, and should be explained if necessary (eg, via an audit trail).

- Source documents provide evidence for the existence of the subject and substantiate the integrity of the data collected. Source documents are filed at the investigator's study center.
- Data reported on the eCRF or entered in the eCRF that are transcribed from source documents must be consistent with the source documents or the discrepancies must be explained. The investigator may need to request previous medical records or transfer records, depending on the study. Also, current medical records must be available.
- Definition of what constitutes source data can be found in clinical monitoring plan.

Study and Study Center Closure

The Sponsor designee reserves the right to close the study center or terminate the study at any time for any reason at the sole discretion of the Sponsor. Study centers will be closed upon study completion. A study center is considered closed when all required documents and study supplies have been collected and a study center closure visit has been performed.

The investigator may initiate study center closure at any time, provided there is reasonable cause and sufficient notice is given in advance of the intended termination.

Reasons for the early closure of a study center by the Sponsor or investigator may include but are not limited to:

- Failure of the investigator to comply with the protocol, the requirements of the IEC or local health authorities, the Sponsor's procedures, or GCP guidelines.
- Inadequate recruitment of subjects by the investigator.
- Discontinuation of further study treatment development.

Publication Policy

The data generated by this study are confidential information of the Sponsor. The Sponsor will make the results of the study publicly available. The publication policy with respect to the investigator and study center will be set forth in the Clinical Trial Agreement.

- The results of this study may be published or presented at scientific meetings. If this is foreseen, the investigator agrees to submit all manuscripts or abstracts to the Sponsor before submission. This allows the Sponsor to protect proprietary information and to provide comments.
- The Sponsor will comply with the requirements for publication of study results. In accordance with standard editorial and ethical practice, the Sponsor will generally support publication of multicenter studies only in their entirety and not as individual study center data. In this case, a Coordinating investigator will be designated by mutual agreement.
- Authorship will be determined by mutual agreement and in line with International Committee of Medical Journal Editors authorship requirements.

